2.4 Rationale for Ruxolitinib in CMML

GM-CSF signaling is both dysregulated and important for CMML survival *in vitro* and *in vivo* (see section 2.2). Although GM-CSF signaling is hallmarked by cytokinepleotropy, it appears that STAT5 is preferentially activated in the CMML disease phenotype. Our laboratory has shown that targeting GM-CSF activation leads to decreased viability in primary CMML patient samples. In the late 1990s, efforts were made to target this pathway. Frankel and colleges developed a GM-CSF molecule fused to diphtheria toxin that was highly toxic to CMML myeloid progenitors in 16/20 patient samples tested²⁰. This led to a phase I clinical trial in relapsed/refractory acute leukemias. Unfortunately, unacceptable hepatotoxicity was seen, even at moderate doses of compound, that did not allow for dose escalation²¹.

This hepatotoxicity is now thought to be Kupffer cell mediated.

The JAK kinases are the sentinel kinases responsible for the key phosphorylation event in many cytokine receptors, including GM-CSF. Parganas and colleagues developed a JAK2 deficient murine model that showed that JAK2 is required to elicit GM-CSF mediated signaling²². Considering this, our laboratory explored JAK1/2 pharmacologic inhibition with SD1029 in primary CMML cells. SD-1029 is a selective JAK1/JAK2 (μM IC50) inhibitor that is not available for clinical use and has a similar JAK inhibition profile to ruxolitinib. In 3 CMML patient samples tested, SD-1029 increased apoptosis and decreased viability by ANNEXIN-V and DAPI staining in a dose dependent fashion. None of these patients tested harbored a JAK2V617F mutation. Lastly, Ravandi and colleagues recently published the results of a phase 2 trial using ruxolitinib in refractory leukemias. In this cohort, 4 CMML patients were enrolled to take BID ruxolitinib (dose not available). It is reported that 2/4 CMML patients demonstrated some degree of clinical benefit²³. Although the nature of the benefit was not expounded upon, it provides further proof-of-principle that JAK inhibition may indeed result in responses in this disease. Our preliminary data, in addition to the extensive data demonstrating the role of GM-CSF in CMML, provides compelling evidence to explore JAK1/2 inhibition with ruxolitinib as a therapeutic target in CMML.

2.5 **A phase 1/2 clinical study of ruxolitinib in CMML**

We have performed a phase 1/2 study of ruxolitinib in CMML. This study included any patient with a WHO diagnosis of CMML irrespective of therapy. This phase 1 study identified 20mg PO BID as the maximally tolerated dose of ruxolitinib in CMML and accrued 20 patients²⁴. This study demonstrated broad range activity that was enriched in patients with splenomegaly and disease related symptoms. This was confirmed in the phase 2 study which accrued 29 patients and has presented in abstract form. Therefore, this phase 2 expansion will explore efficacy in only those CMML patients with either symptomatic splenomegaly and/or disease related symptoms defined by a Total Symptom Score of ≥ 17 .

3 STUDY ENDPOINTS

3.1 Primary

3.1.1 Proportion of subject achieving clinical benefit defined as hematologic improvement, complete remission, partial remission, or stable disease by the IWG MDS/MPN criteria at week 16 (see section 14)

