
Study Endpoints
	
Primary:
 
 Proportion of subject achieving clinical benefit defined as hematologic improvement, complete remission, partial remission, or stable disease by the IWG MDS/MPN criteria at week 16 
Secondary
 
 Acute myeloid leukemia (AML) transformation according to WHO criteria. Overall survival (OS). Duration of response. The Myeloproliferative Neoplasms Symptom Assessment Form (MPN-SAF TSS Total Symptom Score at baseline and at week 16. ≥35% decrease in splenic volume as measured by CT Scan if applicable Mutational status in our CMML patients by sanger sequencing of JAK2, c-CBL, N-RAS, K-RAS, RUNX-1, TET2, SRSF2, EZH2, ASXL1, and DNMT3a (pretreatment and progression). Changes in cytokine secretion of peripheral blood at baseline and week 16 as previously described¹.

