1 OBJECTIVES

1.1 Primary Objective:

To determine overall response rates as measured by the international working group MDS/MPN criteria.

1.2 Secondary Objectives:

1.2.1 To determine the time to AML transformation of patients on ruxolitinib.

1.2.2 To determine the median overall survival.

1.2.3 To determine the duration of response achieved as in secondary endpoint one.

1.2.4 To determine the change in symptom score from baseline to week 16.

1.2.5 To determine the change in spleen volume at 16 weeks.

1.2.6 To determine if a correlation exist between the presence of the known recurrent mutations (JAK2, c-CBL, N-RAS, K-RAS, RUNX-1, TET2, SRSF2, EZH2, ASXL1, and DNMT3a) and response to ruxolitinib.

1.2.7 To determine if a correlation exists between inflammatory cytokine secretion in the peripheral blood and response to ruxolitinib in CMML patients.

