5 STUDY DESIGN

This is a phase 2, Simon's two stage design. A total of 10 patients will be treated during the first stage of phase 2 (stage 1) at 20mg BID. The trial will be terminated if 1 or fewer respond. If the trial goes on to the second stage, a total of 29 patients will be studied to determine efficacy in phase 2.

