14 MEASUREMENT OF EFFECT

Definitions:

Response and progression will be assessed according to modified International Working Group (IWG) MDS/MPN criteria (see section 14).

Complete Response (CR)

1. Bone Marrow:
 - a. $\leq 5\%$ myeloblasts and promonocytes
 - b. \leq grade 1 reticulin fibrosis
2. Peripheral Blood:
 - a. $\text{WBC} \leq 10 \times 10^9$ cells/L
 - b. $\text{Hgb} \geq 11$ g/dL
 - c. $\text{Platelets} \geq 100 \times 10^9$ cells/L
 - d. Blasts 0%
 - e. Neutrophil precursors $\leq 2\%$
 - f. $\text{Monocytes} \leq 1 \times 10^9$ cells/L
3. Extramedullary Disease
 - a. Complete resolution of extramedullary disease present before therapy including palpable hepatosplenomegaly

Complete Cytogenetic Response

Resolution of previously present chromosomal abnormalities as seen on G band cytogenetics.

Partial Response

Normalization of peripheral counts and hepatosplenomegaly with bone marrow myeloblasts reduced by 50% but remaining $>5\%$ of cellularity except in cases of MDS/MPN with $\leq 5\%$ bone marrow blasts at baseline

Marrow Response

Optimal marrow response: Presence of all CR marrow criteria without normalization of peripheral blood indices.

Partial marrow response: Bone marrow blasts reduced by 50% but remaining $>5\%$ of cellularity **or** reduction in grading of reticulin fibrosis from baseline on at least 2 bone marrow evaluations at least 2 months apart.

Clinical Benefit

Requires 1 of the following in the absence of progression or CR/partial response and independent of marrow response to be considered clinical benefit.

1. Erythroid Response: a) Hgb increase by ≥ 2.0 g/dL b) TI for ≥ 8 wk for patients requiring at least 4 packed red blood cell transfusions in the previous 8 wk
Only red blood cell transfusions given based on physician's judgment for a pretreatment Hgb of ≤ 8.5 g/dL will count in the red blood cell TI response evaluation
2. Platelet response: a) Transfusion independence when previously requiring platelet transfusions of at least a rate of 4 platelet transfusions in the previous 8 wk. b) Pretreatment $\leq 20 \times 10^9$ /L: increase from $< 20 \times 10^9$ /L to $> 20 \times 10^9$ /L and by at least 100% c) Pretreatment $> 20 \times 10^9$ /L but $\leq 100 \times 10^9$ /L: absolute increase of $\geq 30 \times$

$10^9/L$

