15 STATISTICAL CONSIDERATIONS

15.1 Study Design

This will be a two stage Simon's phase 2 design. After testing the treatment dose on 10 patients in the first stage, the trial will be terminated if 1 or fewer achieve a clinical benefit. If the trial goes on to the second stage, a total of 29 patients will be studied. If the total number responding is less than or equal to 5, the drug is rejected.

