15.2 Sample Size/Accrual Rate

The Simon's optimal two-stage design will be employed to test the null hypothesis that response rate (RR) is less than 10% versus the alternative that RR greater or equal to 30%. If the treatment is actually not effective, there is a 0.05 probability of concluding that it is. If the drug is actually effective, there is a 0.19 probability of concluding that it is not. The probability of early terminating the trial at the end of first stage under the null is 0.74. After testing the treatment dose on 10 patients in the first stage, the trial will be terminated if 1 or fewer desired respond. If the trial goes on to the second stage, a total of 29 patients will be studied. If the total number responding is less than or equal to 5, the drug is rejected. A sample size of 29 from Phase 2 produces a two-sided 95% CI with a width equal to 0.38 (± 19) when the sample proportion is 0.50 that is the maximum width for a CI with an given sample sizes.

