15.5 Efficacy Analysis: ITT

This analysis will include all patients who have received any protocol treatment, regardless of patient eligibility or duration of treatment. Those who have no response assessment data due to reasons such as drop out of the study, withdrawal consent, or lost to follow-up will be treated as non-responders for various response evaluations. The proportion of patients achieving a response will be

summarized. A 95% exact binomial confidence interval of the proportion will also be provided for all participants treated at the 20mg BID. In addition, a second analysis of evaluable patients will be performed. Evaluable patients are defined as those who complete at least 8 weeks of therapy and complete their first treatment bone marrow biopsy and aspirate to evaluate study drug response.

16 Laboratory Correlates

Unless otherwise specified, all laboratory correlates will be performed in the laboratory of [name].

H.LEE MOFFITT CANCER CENTER

CC: [name]

STABILE RESEARCH BUILDING

[name]

[name]

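### The primary endpoint in Section 3.1.1 counts stable disease as success, but Section 14 and the 10% versus 30% Simon test do not

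*Combined protocol and SAP*

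**What the plan says.** **Endpoint.** Section 3.1.1 sets the primary endpoint as the proportion of patients with "clinical benefit defined as hematologic improvement, complete remission, partial remission, or stable disease by the IWG MDS/MPN criteria at week 16 (see section 14". The synopsis repeats the key phrase: "or stable disease by the IWG MDS/MPN criteria at week 16".

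**Definition referred to.** In Section 14, clinical benefit "Requires 1 of the following in the absence of progression or CR/partial response and independent of marrow response to be considered clinical benefit". The list that follows has five items: erythroid, platelet, neutrophil, spleen and symptom response. Stable disease is not listed and no criterion for it is given.

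**Hypotheses and cut-offs.** Section 15.2 tests the "null hypothesis that response rate (RR) is less than 10% versus the alternative that RR greater or equal to 30" percent. Stage 1 stops at 1 or fewer of 10, and the drug is rejected at 5 or fewer of 29. The stated properties are a type I error of 0.05, a type II error of 0.19 and a 0.74 probability of stopping early under the null.

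**What is counted.** The wording varies:
- Section 1.1: "To determine overall response rates as measured by the international working group MDS/MPN criteria".
- Section 5: "The trial will be terminated if 1 or fewer respond".
- Section 15.1, stage 1: "the trial will be terminated if 1 or fewer achieve a clinical benefit". Its final count is of patients responding.
- Section 15.5: "The proportion of patients achieving a response will be" summarised.

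**Week-16 handling.** Section 7 lets responding patients continue. Section 9.1.1 treats 16 weeks without improvement as study completion. Section 9.3 stops drug when there has been no clinical benefit by then.

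**The concern.** The stage-1 stop and the final decision each rest on a single count, and two analysts could make that count differently from the same data. Section 15.1 gates stage 1 on clinical benefit, which is the term that 3.1.1 widens to include stable disease and Section 14 does not.

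On the literal 3.1.1 reading, a patient who merely fails to progress over 16 weeks counts toward calling the drug active. Cut-offs built for a 10% null response rate are then applied to an event that is broader than response. The futility stop weakens for the same reason: two stable patients among the first ten would carry the trial into stage 2.

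Patient management is affected too. A stable patient at week 16 is a primary success under 3.1.1, yet has not improved (9.1.1) and is not a responder who may continue (Section 7). Whether 9.3 stops that patient's drug depends on which definition of clinical benefit is used.

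**Working it through.** **Inputs.** From Section 15.2: n1 = 10, r1 = 1, n = 29, r = 5, p0 = 0.10, p1 = 0.30. The documents give no rate of stable disease on an inert drug, so the combined rate p (responding or stable at week 16) is an assumption, shown from 10% to 50%.

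**Formulas.** With X1 the stage-1 count and X2 the count in the remaining 19 patients, both binomial with probability p:

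- P(early stop) = P(X1 ≤ 1) = (1−p)^10 + 10p(1−p)^9
- P(declare active) = Σ over x = 2 to 10 of P(X1 = x) · P(X2 ≥ 6 − x)

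**Step 1: reproduce the plan's figures.** At p = 0.10:

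- P(early stop) = 0.3487 + 0.3874 = 0.7361 (stated 0.74).
- P(declare active) = 0.1937×0.1150 + 0.0574×0.2946 + 0.0112×0.5797 + 0.0015×0.8649 + about 0.0002 = 0.0471 (stated 0.05).

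At p = 0.30, P(declare active) = 0.8051, so the type II error is 0.195 (stated 0.19). The stated design is therefore correct for an event with a 10% null rate.

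**Step 2: same cut-offs, higher inert-drug rate.** At p = 0.20, for example, P(early stop) = 0.1074 + 0.2684 = 0.3758.

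| Assumed inert-drug rate (response plus stable) | P(declare active) | P(early stop) |
|---|---|---|
| 10% | 0.047 | 0.736 |
| 15% | 0.201 | 0.544 |
| 20% | 0.431 | 0.376 |
| 30% | 0.805 | 0.149 |
| 40% | 0.950 | 0.046 |
| 50% | 0.989 | 0.011 |

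**Step 3: where protection is lost.** Solving the same expressions for p:

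- P(declare active) reaches 0.05 at p = 10.15%.
- P(early stop) falls to one half at p = 16.2%.
- P(declare active) reaches one half at p = 21.5%.

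The design has almost no room for a null rate above 10%.

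**Step 4: what keeping stable disease would require.** Holding stage 1 at 1/10 and n at 29, the smallest final cut-off r (reject at r or fewer) that keeps P(declare active) at or below 0.05 is:

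| Inert-drug rate | r | P(declare active) |
|---|---|---|
| 20% | 9 | 0.047 |
| 30% | 13 | 0.029 |
| 40% | 16 | 0.033 |
| 50% | 19 | 0.031 |

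The plan's r is 5.

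**Step 5: could the 10% already include stable disease?** No section says so. Section 15.2 attaches it to response rate. The closest figure in the background, 10–15% with azacitidine in the myeloproliferative variant (Section 2.1), is also a response rate.

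**The case against.** The best counter-argument is that Section 14 plainly governs and the phrase in 3.1.1 is stray wording with one copy in the synopsis. The primary objective, Section 5, Section 15.2, Section 15.5 and the final count in 15.1 all speak of response, as does the synopsis accrual rule. Section 3.1.1 itself sends the reader to Section 14. The week-16 rules also agree with each other under Section 14: a merely stable patient has not improved, is not responding and has no clinical benefit, so drug stops. On this view the false-positive figures depend on a less-supported reading and on a stable-disease rate the documents do not give.

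Much of that is fair. Section 14 is probably what was meant, and the inflation is conditional on both points. But the phrase sits in the formal statement of the primary endpoint and is repeated in the synopsis, and no text gives Section 14 precedence. An analyst who follows the endpoint as written would feed stable patients into the Simon counts.

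Two narrower objections concern the remedy. First, even under Section 14 the stated error rates hold only if 10% is a sound null for the composite, which includes a 50% symptom reduction in an uncontrolled study. That stands, and the fix asks for the justification. Second, naming spleen and symptom response, which 3.1.1 does not list, might raise the success count. That does not stand against 3.1.1 as written: a spleen or symptom responder without progression would already count there as at least stable.

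**Conclusion.** The concern holds and should be fixed before outcome data are analysed. The primary endpoint as written does not match the definition it refers to or the event for which the Simon cut-offs were derived.

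The size depends on the reading. If Section 14 governs, there is no inflation from this source. If 3.1.1 is applied literally, the type I error exceeds 0.05 once the inert-drug rate of response plus stable disease passes about 10.2%, and at an assumed 20% to 50% it lies between 0.43 and 0.99. These rates are assumptions; the true one is unknown. The arithmetic is exact for the stated cut-offs and assumes independent patients with a common rate.

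**What to change.** - Delete stable disease from the endpoint in 3.1.1 and the synopsis.
- Define one primary response: CR, PR, or at least one Section 14 clinical-benefit criterion (erythroid, platelet, neutrophil, spleen or symptom) at week 16. State that marrow response alone does not count.
- Use that term in 1.1, 5, 15.1, 15.2 and 15.5 for both the stage-1 and final counts, and in 7, 9.1.1 and 9.3 for the week-16 continuation rule.
- Give in 15.2 the basis for 10% as the null rate of this composite.
- Report stable disease separately and descriptively, with its criterion written into Section 14.

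N = 29 and the cut-offs 1/10 and 5/29 stay.

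**Cost.** A protocol amendment to the primary endpoint, made before outcome data are analysed so that the result cannot choose the definition. No new patients or assessments are needed: blood counts, transfusion log, CT, symptom score and marrow are already scheduled, so patients already assessed can be classified from collected data. The reported proportion will be lower than with stable disease counted. The documents do not show whether the stage-1 decision had been taken by Version 5. If it had, the amendment should record which definition was used for it.

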3.2 Secondary

3.2.1 Acute myeloid leukemia (AML) transformation according to WHO criteria.

3.2.2 Overall survival (OS).

3.2.3 Duration of response.

3.2.4 The Myeloproliferative Neoplasms Symptom Assessment Form (MPN-SAF TSS) Total Symptom Score at baseline and at week 16.

3.2.5 $\geq 35\%$ decrease in splenic volume as measured by CT Scan if applicable

3.2.6 Mutational status in our CMML patients by sanger sequencing of JAK2, c-CBL, N-RAS, K-RAS, RUNX-1, TET2, SRSF2, EZH2, ASXL1, and DNMT3a (pretreatment and progression).

3.2.7 Changes in cytokine secretion of peripheral blood at baseline and week 16 as previously described¹.

4 PATIENT SELECTION / Eligibility Criteria

4.1 Inclusion criteria

4.1.1 Confirmed diagnosis of CMML using the World Health Organization (WHO) classification (appendix D).

4.1.2 Age >18 years at the time of obtaining informed consent.

4.1.3 Must be able to adhere to the study visit schedule and other protocol requirements.

4.1.4 Patients must be able to provide adequate BM aspirate and biopsy specimens for histopathological analysis and standard cytogenetic analysis during the screening procedure.

4.1.5 An Eastern Cooperative Oncology Group (ECOG) performance status score of 0, 1, or 2 is required.

4.1.6 Women of childbearing potential must have a negative pregnancy test at time of screening and baseline visits and agree to use two reliable forms of contraception

simultaneously or to practice complete abstinence from heterosexual intercourse 1) for at least 28 days before starting study drug; 2) while participating in the study; and 3) for at least 28 days after discontinuation from the study. The two methods of reliable contraception must include one highly effective method (i.e. intrauterine device [IUD], hormonal [birth control pills, injections, or implants], tubal ligation, partner's vasectomy) and one additional effective (barrier) method (i.e. latex condom, diaphragm, cervical cap).

4.1.7 Must understand and voluntarily sign an informed consent form.

4.1.8 Must have a life expectancy of greater than 3 months at time of screening.

4.1.9 Must have symptomatic splenomegaly and/or an MPN-SAF TSS >17.

4.2 Exclusion Criteria

4.2.1 Any of the following lab abnormalities:

4.2.1.1 Platelet count of less than 35,000/uL

4.2.1.2 Absolute Neutrophil Count (ANC) of less than 250 cells/uL

4.2.1.3 Serum Creatinine ≥ 2.0

4.2.1.4 Serum total bilirubin $> 1.5 \times \text{ULN}$

4.2.2 Use of cytotoxic chemotherapeutic agents, or experimental agents (agents that are not commercially available) for the treatment of CMML within 28 days of the first day of study drug treatment.

4.2.3 Any serious medical condition or psychiatric illness that will prevent the subject from signing the informed consent form or will place the subject at unacceptable risk if he/she participates in the study.

4.2.4 Concurrent use of GM-CSF. G-CSF could be used for the short-term management of neutropenic infection. Stable doses of erythropoietin stimulating agents that were started > 8 weeks from first ruxolitinib dose or corticosteroids that were being administered prior to screening are allowed.

4.2.5 Uncontrolled current illness including, but not limited to ongoing or active infection, symptomatic congestive heart failure, unstable angina pectoris, cardiac arrhythmia, or psychiatric illness/social situations that would limit compliance with study requirements.

- 4.2.6 History of metastatic malignancy in the preceding 2 years.
- 4.2.7 Pregnant women are excluded from this study because ruxolitinib has not been studied in pregnant patients. Because there is an unknown but potential risk for adverse events in nursing infants secondary to treatment of the mother with ruxolitinib, breastfeeding should be discontinued if the mother is treated with ruxolitinib.

4.3 Inclusion of Women and Minorities

Both men and women and members of all races and ethnic groups are eligible for this trial.

5 STUDY DESIGN

This is a phase 2, Simon's two stage design. A total of 10 patients will be treated during the first stage of phase 2 (stage 1) at 20mg BID. The trial will be terminated if 1 or fewer respond. If the trial goes on to the second stage, a total of 29 patients will be studied to determine efficacy in phase 2.

6 TREATMENT PLAN

6.1 Ruxolitinib administration

All patients will self-administer ruxolitinib twice daily, 12 hours apart as an outpatient. On all days corresponding to study visits, patients will take the morning dose of study drug prior to the visit, and will note on the subject reminder card the time that medications were taken. Reported adverse events and potential risks are described in Section 11. Appropriate dose modifications for ruxolitinib are described in Section 10. No investigational or commercial agents or therapies other than those described below may be administered with the intent to treat the patient's CMML.

6.1.1 Ruxolitinib will be supplied by INCYTE as tablets that will be self-administered BID orally, with or without food approximately 12 hours apart (morning and night).

6.1.2 The dosage strength is 5 mg/tablet ruxolitinib phosphate (free base equivalent). Administration instructions will be provided at Study Visits. The administration instructions will state that medication is "For Investigational Use Only". Ruxolitinib 5 mg tablets are packaged as 60 count in high-density

polyethylene (HDPE) bottles. The bottles will include labeling “New Drug - Limited by Federal (USA) Law to Investigational Use. The bottles of tablets should be stored at room temperature, 15°C to 30°C (59°F to 86°F).

